### **The risks and hazards of emtricitabine therapy**

More than 2000 adult patients with HIV infection have been treated with emtricitabine either alone or in combination with other antiretroviral agents for periods of 10 days to 200 weeks in Phase I-III clinical trials. Assessment of adverse reactions is based on data from studies 301A and 303 in which 571 treatment naïve (301A) and 440 treatment experienced (303) patients received emtricitabine 200mg (n=580) or comparator drug (n=431) for 48 weeks. The most common adverse events that occurred in patients receiving emtricitabine with other antiretroviral agents in clinical trials were headache, diarrhea, nausea and rash that were generally of mild to moderate severity.

Approximately 1% of patients discontinued participation in the clinical trials due to these events. All adverse events were reported with similar frequency in emtricitabine and control treatment groups with the exception of skin discoloration which was reported with higher frequency in the emtricitabine treated group. Skin discoloration manifested

by hyperpigmentation on the palms and /or soles were generally mild and asymptomatic. The mechanism and clinical significance are unknown.

Selected treatment emergent adverse events (all grades regardless of causality) reported in  $\geq 3\%$  of emtricitabine-treated patients in either study 301A or 303 include abdominal pain 8-14% vs. 11-17%, asthenia 12-16% vs. 10-17%, headache 13-22% vs. 6-25%, diarrhoea 23% vs. 18-32%, dyspepsia 4-8% vs. 5-12%, nausea 13-18% vs. 12-23%, vomiting 9% vs. 7-12%, arthralgia 3-5% vs. 4-6%, myalgia 4-6% vs. 3-4%, abnormal dreams 2-11% vs. <1%-19%, depressive disorders 6-9% vs. 10-13%, dizziness 4-25% vs. 5-26%, insomnia 7-16% vs. 3-21%, neuropathy/peripheral neuritis 4% vs. 3-13%, paresthesias 5-6% vs. 3-13%, increased cough 14% vs. 8-11%, rhinitis 12-18% vs. 10-12% and skin rash 17-30% vs. 14-33% compared to comparator arm respectively. Treatment emergent grade  $\frac{3}{4}$  laboratory abnormalities reported in  $>1\%$  of emtricitabine treated patients in either study 301A or 303 included ALT  $>5X$  ULN 2% vs. 1%, AST  $>5X$  ULN 3% vs. <1%, bilirubin  $>2.5 X$  ULN 1% vs. 2%, creatine kinase  $>4$  ULN 11% vs. 14%, neutropenia  $<750$  mm^3 5% vs. 3%, pancreatic enzyme elevation either amylase or lipase 1-2% vs. <1-2%, serum glucose 3% vs. 3% and triglycerides 10% vs. 8% compared to comparator arm.

Emtricitabine carries a black box warning advising of lactic acidosis and severe hepatomegaly with steatosis including death associated with its use.

Emtricitabine was evaluated in a randomized placebo controlled trial in 167 patients with chronic hepatitis B. The incidence of clinical adverse events during treatment was similar in the 2 groups. Severe (grade 3 or 4) adverse events were reported in 14 (8%) of 167 emtricitabine-treated patients and 7 of 81 patients given placebo (9%), and serious adverse events occurred in 8% (n = 13) and 9% (n = 7), respectively. Related serious adverse events were rare, 4 (2%) of 167 emtricitabine and 3 (4%) of 81 placebo patients. During treatment, the incidence of grade 3 or 4 laboratory abnormalities was significantly reduced in the emtricitabine group, 31 (19%) of 167 patients vs. 33 (41%) of 81 in the placebo group (P<.001), which was due to the lower incidence of grade 3 or 4 transaminase, ALT (7% emtricitabine [n = 11], 26% placebo [n = 21]) and aspartate aminotransferase (2% emtricitabine [n = 3], 12% placebo [n = 10]) (P $\leq$ .001).

Post treatment follow-up safety data were available from 145 patients in the emtricitabine group (median follow-up, 110 days) and 63 patients in the placebo group. Post treatment exacerbation of CHB developed in 33 patients (23%) who had received emtricitabine and 3 placebo patients (5%) (P = .001), with a median time to onset of 10 weeks following the end of treatment (interquartile range, 8-16 weeks). One patient randomized to emtricitabine with marked bridging fibrosis at entry developed severe icteric post treatment exacerbation of CHB and required liver transplantation. All other patients recovered without clinical complications (overall, 14 with and 19 without antiviral therapy).

Long-term carcinogenicity studies of emtricitabine in rats and mice are in progress. Emtricitabine was not toxic in the reverse bacterial test (Ames test), mouse lymphoma or mouse micronucleus assays.

Emtricitabine did not affect fertility in male rats at approximately 140-fold or in male and female mice at approximately 60-fold higher exposures than in humans given the recommended 200 mg dose. Fertility was normal in the offspring of mice exposed daily from before birth (in utero) through sexual maturity at daily exposures of approximately 60-fold higher exposures than in humans given the recommended 200 mg dose.

The incidence of fetal variations and malformations was not increased in embryonal toxicity studies performed with emtricitabine in mice at exposures approximately 60 fold higher and in rabbits at approximately 120 fold higher than in humans exposures given the recommended 200 mg dose. There are however, no adequate and well-controlled studies in pregnant women.

### **The risks and hazards of tenofovir and emtricitabine combination therapy**

Four hundred and forty-seven HIV-1 infected patients have received combination therapy with Emtriva and Viread with either a non-nucleoside reverse transcriptase inhibitor or protease inhibitor for 48 weeks in clinical studies. In study 934, a randomized, open-label, active controlled multicenter study comparing Emtriva and Viread administered in combination with efavirenz versus zidovudine/lamivudine fixed-dose combination administered in combination with efavirenz in 511 antiretroviral-naïve patients, adverse events observed were generally consistent with those seen in other studies in treatment experienced or treatment-naïve patients receiving Viread and/or Emtriva. Selected treatment emergent adverse events (Grades 2-4) reported in  $\geq 3\%$  in the Emtriva and Viread arm compared to the non-Emtriva and Viread arm include diarrhea 7% vs. 4%, nausea 8% vs. 6%, vomiting 1% vs. 4%, fatigue 7% vs. 6%, sinusitis 4% vs. 2%, upper respiratory tract infections 3% vs. 3%, nasopharyngitis 3% vs. 1%, somnolence 3% vs. 2%, headache 5% vs. 4%, dizziness 8% vs. 7%, depression 4% vs. 7%, insomnia 4% vs. 5%, abnormal dream 4% vs. 3%, skin rash 5% vs. 4%. Laboratory abnormalities observed in this study were generally consistent with those seen in other studies of tenofovir and/or emtricitabine. Significant laboratory abnormalities reported in  $\geq 1\%$  of patients in any treatment arm (tenofovir/emtricitabine arm 25% vs. non-tenofovir/emtricitabine arm 22%) included elevated fasting cholesterol 15% vs. 17%, elevated creatine kinase 7% vs. 6%, elevated amylase 7% vs. 3%, elevated AST 3% vs., 2%, elevated ALT 2% vs. 2%, hemoglobin  $< 8$  mg/dl 0% vs., 3%, hyperglycemia 1% vs. 1%, hematuria 2% vs. 2%, neutropenia 3% vs. 4% and elevated fasting triglycerides 4% vs. 2%.

In addition to the events described above for Study 934, other adverse events that occurred in  $> 5\%$  of patients receiving emtricitabine with other antiretroviral agents in clinical trials include abdominal pain, asthenia, arthralgia, increase cough, depressive disorder, dyspepsia, myalgia, paresthesia, rhinitis and rash event (including rash, pruritus, maculopapular rash, urticaria, vesiculobullous rash, pustular rash and allergic reaction).

Skin discoloration has been reported with higher frequency among emtricitabine treated patients. Skin discoloration, manifested by hyperpigmentation on the palms and/or soles was generally mild and asymptomatic. The mechanism and clinical significance are unknown. No additional adverse events were reported in post marketing experience with emtricitabine.

In addition to the laboratory abnormalities described above for study 934, grade 3/4 elevations of bilirubin ( $>2.5 \times \text{ULN}$ ), pancreatic amylase ( $>2.0 \times \text{ULN}$ ), serum glucose ( $<40$  or  $>250$  mg/dL) and serum lipase ( $>2.0 \times \text{ULN}$ ) occurred in  $<1-3\%$  of patients treated with emtricitabine.

In addition to the events described above for study 934, other adverse events that occurred in  $\geq 5\%$  of patients receiving tenofovir with other antiretroviral agents in clinical trials include arthralgia, anxiety, fever, pain, abdominal pain, back pain, peripheral neuritis, peripheral neuropathy, and pneumonia.

In addition to the laboratory abnormalities described above for study 934, grade 3/4 elevations of urine glucose ( $\geq 3+$ ) occurred in 3% of patients receiving tenofovir with other antiretroviral agents in clinical trials the following events have been identified during post-approval use of tenofovir. Because they are reported from a population of unknown size, estimates of frequency cannot be made. These events include allergic reactions, hypophosphatemia, lactic acidosis, dyspnoea, abdominal pain, increased amylase, pancreatitis, increased liver enzymes, hepatitis, renal insufficiency, renal failure, acute renal failure, Fanconi syndrome, proximal tubulopathy, proteinuria, increased creatinine, acute tubular necrosis, nephrogenic diabetes insipidus, polyuria and nephritis.

The combination of tenofovir and emtricitabine carries a black box warning as for tenofovir and other nucleos(t)ide analogues highlighting that lactic acidosis and severe hepatomegaly with steatosis, including fatal cases, have been reported with the use of nucleos(t)ide analogs alone or in combination with other antiretrovirals. A majority of these cases have been in women. Obesity and prolonged nucleoside exposure may be risk factors. Particular caution should be exercised when administering nucleoside analogs to any patient with known risk factors for liver disease; however, cases have also been reported in patients with no known risk factors.

A major safety concern with tenofovir is renal impairment. Cases of acute renal failure and Fanconi syndrome (renal tubular injury with severe hypophosphatemia) have been reported in association with the use of tenofovir. The majority of these cases occurred in patients with underlying systemic or renal disease, or in patients taking nephrotoxic agents, however, some cases occurred in patients without identified risk factors. Patients will be monitored by a series of tests for renal toxicity including calculated GFR using the Modification of Diet in Renal Disease (MDRD) formula, urine analysis and serum phosphate. Dose adjustments or cessation will be based upon any of the following criteria:

1) Absolute decline in GFR by 25 mls/min/1.73 m^2 confirmed on two occasions 2 weeks apart. GFR will be calculated using the Modification of Diet in Renal Disease (MDRD)

formula: (MDRD GFR (ml/min/1.73m^2=170 x[PCr]-0.999 X [Age]-0.176 X [.0762 if patient is female] X [1.180 if patient is black] X [SUN]-0.170 X[Alb]+0.318 where PCr=serum creatinine concentration (mg/dl) (alkaline picrate method); SUN=serum urea nitrogen concentration (mg/dl) (urease method); Alb=serum albumin concentration (g/dl) (bromocresol green method)).

2) Abnormality in any one of the following 4 parameters calculated GFR, urine glucose, serum phosphate and a routine urine analysis will trigger a formal renal evaluation. This will include including assessment of GFR by 24 urine hour creatinine clearance, urine glucose, fractional excretion of phosphate, 24 hour urine for amino acids and serum uric acid, If the evaluation is consistent with Fanconi's syndrome, patients will be discontinued from therapy indefinitely.

3) For Grade 1 toxicity serum creatinine  $\geq .5$  above baseline, the patient will be monitored weekly until the creatinine returns to baseline or  $\leq 0.3$  mg/dL of the baseline value. For confirmed Grade 2 and  $\geq 0.5$  increases from baseline, therapy will be permanently discontinued.

In a 144-week study of HIV positive treatment naïve patients, decreases in bone mineral density (BMD) were seen at the lumbar spine and hip in both arms of the study (study 903 see above). At Week 144, there was a significantly greater mean percentage decrease from baseline in BMD at the lumbar spine in patients receiving tenofovir plus lamivudine plus efavirenz compared with patients receiving stavudine plus lamivudine plus efavirenz. Changes in BMD at the hip were similar between the two treatment groups. In both groups, the majority of the reduction in BMD occurred in the first 24–48 weeks of the study and this reduction was sustained through 144 weeks. Twenty-eight percent of tenofovir-treated patients vs. 21% of the comparator patients lost at least 5% of BMD at the spine or 7% of BMD at the hip. Clinically relevant fractures (excluding fingers and toes) were reported in 4 patients in the tenofovir group and 6 patients in the comparator group. Tenofovir disoproxil fumarate was associated with significant increases in biochemical markers of bone metabolism (serum bone-specific alkaline phosphatase, serum osteocalcin, serum C-telopeptide, and urinary N-telopeptide), suggesting increased bone turnover. Serum parathyroid hormone levels and 1,25 Vitamin D levels were also higher in patients receiving tenofovir. The effects of tenofovir-associated changes in BMD and biochemical markers on long-term bone health and future fracture risk are unknown.

The risk of carcinogenesis, mutagenesis and impairment in fertility has been studied. Long-term oral carcinogenicity studies of tenofovir in mice and rats were carried out at exposures up to approximately 16 times (mice) and 5 times (rats) those observed in humans at the therapeutic dose for HIV infection. At the high dose in female mice, liver adenomas were increased at exposures 16 times that in humans. In rats, the study was negative for carcinogenic findings at exposures up to 5 times that observed in humans at the therapeutic dose.

Tenofovir was mutagenic in the in vitro mouse lymphoma assay and negative in an in vitro bacterial mutagenicity test (Ames test). In an in vivo mouse micronucleus assay tenofovir was negative when administered to male mice.

There were no effects on fertility, mating performance or early embryogenic development when tenofovir was administered to male rats at a dose equivalent to 10 times the human dose based on body surface area comparisons for 28 days prior to mating and to female rats for 15 days prior to mating through day seven of gestation. There was however an alteration of the estrous cycle in female rats.

The incidence of fetal variations and malformations was not increased in embryofetal toxicity studies performed with emtricitabine in mice at exposures (AUC) approximately 60-fold higher than human exposures at the recommended daily dose.

Reproduction studies have been performed in rats and rabbits at doses up to 14 and 19 times the human dose based on the body surface area comparisons and revealed no evidence of impaired fertility or harm to the fetus due to tenofovir. There are however, no adequate and well-controlled studies in pregnant women.

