ii) **Toxicity.** Either intolerance to tenofovir or the combination of tenofovir and emtricitabine or development of worsening renal function would be a reason to stop therapy (see below **The risks and hazards of tenofovir and emtricitabine combination therapy** for management of tenofovir toxicity.)

In either situation, entecavir or peginterferon would be options for alternative therapy. Discontinuation of therapy due to toxicity will be considered failure of therapy and, if treated, not as a part of this protocol.

iii) **Clearance of HBsAg.** Patients who become and remain HBsAg and HBV DNA negative for at least six months will have therapy discontinued. These patients will be monitored at 4 week intervals for the next 6 months and then every 12 weeks. If HBsAg returns or if HBV DNA levels rise above  $10^4$  IU/ml, therapy will be reinstated. Patients who clear HBsAg who are anti-HBs negative will be given a course of HBV vaccine (0, 1 and 4-6 months).

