Hypophosphatemia	WNL	<LLN -2.5 mg/dL <LLN - 0.8 mmol/L	2.0 - <2.5 mg/dL 0.6 - <0.8 mmol/L	1.0 - <2.0 mg/dL 0.3 - <0.6 mmol/L	<1.0 mg/dL <0.3 mmol/L
Creatinine	WNL	>.5 above baseline	>1.5 - 3.0 x ULN	>3.0 - 6.0 x ULN	>6.0 x ULN
Bicarbonate	WNL	<LLN - 16 mEq/dL	11 - 15 mEq/dL	8 - 10 mEq/dL	<8 mEq/dL
CPK (creatinine phosphokinase)	WNL	>ULN - 2.5 x ULN	>2.5 - 5 x ULN	>5 - 10 x ULN	>10 x ULN
Amylase	WNL	>ULN - 1.5	>1.5 - 2.0 x	>2.0 - 5.0 x	>5.0 x ULN

		x ULN	ULN	ULN	
Lipase	WNL	>ULN - 1.5 x ULN	>1.5 - 2.0 x ULN	>2.0 - 5.0 x ULN	>5.0 x ULN
Sinus bradycardia	None	asymptomatic, not requiring treatment	symptomatic, but not requiring treatment	symptomatic and requiring treatment	life-threatening (e.g., arrhythmia associated with CHF, hypotension, syncope, shock)
Sinus tachycardia	None	asymptomatic, not requiring treatment	symptomatic, but not requiring treatment	symptomatic and requiring treatment of underlying cause	-
Conduction abnormality Atrio-ventricular heart block	None	Asymptomatic, not requiring treatment (e.g. Mobitz type I second-degree AV block, Wenkebach)	Symptomatic, but not requiring treatment	Symptomatic and requiring treatment (e.g. Mobitz type II second degree AV block, third degree AV block)	Life-threatening (e.g. arrhythmia associated with CHF, hypotension, syncope, shock)
Supraventricular arrhythmias (SVT/atrial fibrillation/flutter)	None	asymptomatic, not requiring treatment	symptomatic, but not requiring treatment	symptomatic and requiring treatment	life-threatening (e.g., arrhythmia associated with CHF, hypotension, syncope, shock)
Cardiac-ischemia/infarction	None	non-specific T-wave flattening or changes	asymptomatic, ST- and T-wave changes suggesting ischemia	angina without evidence of infarction	acute myocardial infarction

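### The printed GFR formula multiplies women's values by .0762, so the renal criterion of a 25-unit fall cannot work for typical women

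*Combined protocol and SAP*

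**What the plan says.** Section G, in the subsection on the risks of combination therapy, names renal impairment as a major safety concern and says patients will be monitored by tests that include "calculated GFR using the Modification of Diet in Renal Disease (MDRD) formula". Dose adjustment or cessation then rests on any of three criteria.

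- **Criterion 1:** "Absolute decline in GFR by 25 mls/min/1.73" m², confirmed on two occasions two weeks apart. The formula is printed here. Its sex and race factors, after a leading decimal point, read "0762 if patient is female] X [1.180 if patient is black".
- **Criterion 2:** "Abnormality in any one of the following 4 parameters calculated GFR", urine glucose, serum phosphate or urinalysis "will trigger a formal renal evaluation". No cut-off for GFR is given.
- **Criterion 3:** at Grade 1 creatinine toxicity (a rise of 0.5 over baseline), "the patient will be monitored weekly until the creatinine returns to baseline" or near it. A confirmed Grade 2 rise means permanent discontinuation. Appendix B, Table 1 defines Grade 1 creatinine as ">.5 above baseline".

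Exclusion criterion 13 in Section B bars patients with a creatinine clearance below 50 ml/min or a serum creatinine above 1.3 mg/dl. No other section gives a different female factor.

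**The concern.** A female factor of .0762 makes a woman's GFR about one-thirteenth of that of a man with the same age and blood values. This cannot be squared with the protocol's own entry rule. A woman admitted with a measured clearance of at least 50 would be assigned a calculated GFR in single figures. Measured clearance and calculated GFR are different quantities, but not by that much.

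Criterion 1 is an absolute fall, so it depends on the scale. If the baseline is below 25, no loss of renal function, however severe, can meet it. Criterion 2 is affected in the opposite direction: a value near 8 looks abnormal whether or not anything has changed. At stake is whether one of the three on-treatment renal rules works for women on a drug they take for years.

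**Working it through.** **Inputs.** The formula, the fall of 25 and the creatinine rise of 0.5 come from Section G. The entry limits come from Section B, and the expected share of women (10–20%) from Section N. The documents describe no typical woman, so age 45, creatinine (Cr) 0.8, urea nitrogen (SUN) 14 and albumin (Alb) 4.0 are assumptions, varied below. The protocol reports no worked GFR to reproduce.

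**Formula.** GFR = 170 × Cr^−0.999 × Age^−0.176 × F × (1.180 if black) × SUN^−0.170 × Alb^0.318, where F is the female factor.

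**Step 1: the example patient.** Without F: 170 × 1.2497 × 0.5117 × 0.6385 × 1.5540 = 107.9, the value for a man.

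- Printed factor: 107.9 × .0762 = 8.2. The ratio of man to woman is 1/.0762 = 13.1.
- Decimal moved one place: 107.9 × .762 = 82.2.

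**Step 2: can criterion 1 be met?** From 8.2 the largest possible fall is 8.2. For a woman of this age, urea nitrogen and albumin, the printed GFR equals 25 only at a baseline creatinine of 0.26 (0.31 with the 1.180 factor).

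**Step 3: other women.** Assumed ranges are age 19–75, urea nitrogen 5–25 and albumin 3.0–5.5.

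| Baseline creatinine | Printed GFR | With 1.180 |
|---|---|---|
| 0.5–1.3 | 3.8–20.2 | 4.5–23.8 |
| down to 0.4 | maximum 25.2 | maximum 29.7 |
| down to 0.3 | maximum 33.6 | maximum 39.7 |

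No baseline reaches 25 when creatinine is 0.5 or more. The protocol sets no lower creatinine limit, so exceptions exist at the extreme. At age 19, creatinine 0.3, urea nitrogen 5 and albumin 5, the printed GFR is 32.6 and criterion 1 would fire at creatinine 1.29. With the 1.180 factor the figures are 38.5 and 0.86.

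**Step 4: what women lose.** With F = .762, age 45, urea nitrogen 14 and albumin 4.0, a fall of 25 from baseline G₀ occurs at Cr₁ = Cr₀ × [G₀/(G₀ − 25)]^(1/0.999). For Cr₀ = 0.8 this is 0.8 × (82.2/57.2)^(1/0.999) = 1.15. Criterion 3 starts weekly monitoring at Cr₀ + 0.5.

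| Baseline Cr | Corrected criterion 1 acts at | Criterion 3 monitoring starts at |
|---|---|---|
| 0.6 | 0.78 | 1.1 |
| 0.7 | 0.95 | 1.2 |
| 0.8 | 1.15 | 1.3 |
| 0.9 | 1.37 | 1.4 |

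At each point in the middle column the printed formula shows a fall of 25 × (.0762/.762) = 2.5. The two rules cross at a baseline of about 0.92. The crossing is 1.04 at age 25, SUN 10, Alb 4.5, and 0.83 at age 70, SUN 20, Alb 3.5. Above it, criterion 3 comes first.

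**Step 5: how many.** 10–20% of 100 patients is 10–20 women.

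**The case against.** The best case against is that this is a one-place slip that may never have reached practice. The protocol names the MDRD equation, and staff or a laboratory using a standard implementation would be unaffected. A GFR near 8 in a woman whose measured clearance was at least 50 at entry would probably be questioned. That is fair: nothing in the documents shows which coefficient was used. But the protocol prints this formula as the way GFR will be calculated, so the text needs correcting either way.

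Second, other protection remains. Criterion 3 uses raw creatinine. The phosphate, glucose and urinalysis limbs of criterion 2 and the 24-hour clearances at weeks 48 and 192 (Section E) do not depend on the formula. Section F separately says "development of worsening renal function would be a reason to stop therapy". This stands and limits the harm. It does not repair criterion 1: at Grade 1, criterion 3 brings weekly monitoring only, and at low baselines it starts later.

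Third, the criterion 2 effect depends on reading an abnormality as a low value. If it meant a change from baseline, women would not be flagged at the start. The low-value reading is the more natural one, because the other three limbs are naturally read as abnormal results, but the missing cut-off keeps the point conditional. It is also fair that flagging every woman would lead to measured clearances, which would soon expose the misprint. Over-flagging and a silent criterion 1 are therefore unlikely to persist together for long.

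Finally, 10–20 women is an upper bound. The loss of an earlier trigger applies to those with low baseline creatinine, and the documents give no creatinine distribution.

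**Conclusion.** The concern holds. As printed, the formula makes criterion 1 inoperative for typical eligible women. Across the assumed ranges, no woman with creatinine of 0.5 or more has a baseline from which GFR could fall by 25, and the rule can fire only at extreme creatinine values of about 0.3–0.4. Criterion 2, read as a low value, stops discriminating among women.

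The practical loss is an earlier trigger for women with baseline creatinine below about 0.9, plus needless evaluations if criterion 2 is applied literally. It should be fixed, but it does not threaten the trial's conclusions.

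That the coefficient is wrong follows from the protocol's own clearance limit and needs no outside source. That 0.762 was intended is an inference: the documents do not state it, though it gives a plausible value for the example woman. A text-extraction slip is possible, although the neighbouring coefficients show no corruption.

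**What to change.** Check the source file, verify the female coefficient in Section G against the MDRD equation the protocol names, and correct it. Establish which coefficient was actually used. If any female GFR was computed with .0762, recalculate it and review whether criterion 1 or 2 would have been met. Leave the clinical thresholds unchanged.

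The cost is one corrected number and, at most, a rerun of stored values for the women enrolled. There is no cost to patients, and the sample size and efficacy analysis do not change.

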### **E. Monitoring**

Patients will be seen, interviewed, and have blood and urine tests taken at regular intervals according to the following schedule (Appendix A): on at least two occasions during the six months before treatment (Screen 1 and 2) including at the time of liver biopsy and initial evaluation, on day 0 (before first administration of drug) and at weeks 2, 4, 8, 12, 24, 36, and 48 after starting therapy. Thereafter, the patients will be seen every 12 weeks while on therapy. At each visit, the patients will be asked about symptoms and possible side effects and fill out a symptom and side effect questionnaire. Blood samples will be drawn for CBC and biochemical tests including chemistry-20 panel (ALT, AST, alkaline phosphatase, creatine kinase, lactic dehydrogenase, direct and total bilirubin, sodium, potassium, chloride, bicarbonate, glucose, BUN, creatinine, albumin, total protein, calcium, and phosphate), and 10 ml of research blood. HBV DNA will be measured at every clinical visit during therapy and more often if needed, such as to investigate viral breakthrough. In addition, HBsAg, HBeAg and anti-HBe will be tested every 12 weeks during therapy and anti-HBs if appropriate. An additional sample will be collected for routine storage to allow for repeat testing. Urine will be collected for urinalysis and random total protein/creatinine ratio at every visit. Twenty-four hour urine for creatinine clearance and total protein will be done at 48 weeks and 192 weeks. Women of child bearing potential will have a pregnancy test at each study visit. Women with a positive pregnancy test will be immediately withdrawn from study drug/s. Patients may be offered alternative approved therapy if clinically indicated. Immunological testing for CD4+ and CD8+ T cell responses to HBV antigens will be done before treatment for all previously untreated patients and repeated at 2, 4, 8, 12, 36 and 48 weeks for HLA-A2 positive patients. Alpha-fetoprotein levels will be measured every 24 weeks. Ultrasound or computerized tomography of the liver will be done every 24 weeks months in patients with advanced fibrosis or cirrhosis; in other patients these tests will be done at the time of 48 and 192 week liver biopsies. Fibroscan of the liver will be performed yearly. Bone mineral density will be re-assessed at 48 and 192 weeks.

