study 934, 511 antiretroviral naïve patients received either tenofovir and emtricitabine administered in combination with efavirenz or zidovudine/lamivudine administered in combination with efavirenz. Adverse events and laboratory abnormalities observed in this study were generally consistent with those seen in previous studies in treatment-experienced or treatment naïve patients. In addition to adverse events reported from clinical trials, the following events have been identified during post-approval use of tenofovir. Because they are reported from a population of unknown size, estimates of frequency cannot be made. These events include allergic reactions, hypophosphatemia, lactic acidosis, dyspnoea, abdominal pain, increased amylase, pancreatitis, increased liver enzymes, hepatitis, renal insufficiency, renal failure, acute renal failure, Fanconi syndrome, proximal tubulopathy, proteinuria, increased creatinine, acute tubular necrosis, nephrogenic diabetes insipidus, polyuria and nephritis.

Tenofovir has a black box warning indicating that lactic acidosis and severe hepatomegaly with steatosis including death have been reported with the use of nucleoside analogues alone or in combination with other antiretrovirals. Additionally severe acute exacerbations of hepatitis B have been reported in patients who are coinfecting with HBV and HIV and have discontinued tenofovir. Tenofovir is principally eliminated by the kidney. The dosing interval needs to be adjusted in all patients with creatinine clearance <50 ml/min.

The majority of safety data on tenofovir has come from HIV populations on multidrug regimens. The few series of patients with chronic hepatitis B treated with tenofovir have not reported any serious side effects. The major safety concern with tenofovir is renal impairment. Cases of acute renal failure and Fanconi syndrome (renal tubular injury with severe hypophosphatemia) have been reported in association with the use of tenofovir. The majority of these cases occurred in patients with underlying systemic or renal disease, or in patients taking nephrotoxic agents, however, some cases occurred in patients without identified risk factors.

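### The female factor printed in the MDRD formula (.0762) puts the 25-point GFR decline criterion out of reach for women and makes their calculated GFR look abnormal at every visit

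*Combined protocol and SAP*

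**What the plan says.** The renal rules are in Section G, under the risks of combination therapy. The lead-in reads "Dose adjustments or cessation will be based upon any of the following criteria", and three items follow.

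- **Item 1:** "Absolute decline in GFR by 25 mls/min/1.73" m², confirmed on two occasions two weeks apart. GFR comes from a printed six-variable MDRD equation, in which the sex term is a decimal point followed by "0762 if patient is female".
- **Item 2:** an abnormal calculated GFR, urine glucose, serum phosphate or urinalysis "will trigger a formal renal evaluation". No numeric limit for an abnormal GFR is given. The only stop stated under this item is for Fanconi's syndrome.
- **Item 3:** at a creatinine rise of at least 0.5 from baseline, "the patient will be monitored weekly until the creatinine returns to baseline" or comes within 0.3 mg/dL of it. Confirmed Grade 2 with a rise of at least 0.5 means permanent discontinuation. Appendix B puts Grade 2 at more than 1.5 × ULN.

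Elsewhere, Section F (Stopping therapy, Toxicity) says that "development of worsening renal function would be a reason to stop therapy" and sends the reader back to Section G for management. The tenofovir risk text says "The dosing interval needs to be adjusted in all patients with creatinine clearance <50 ml/min". Section B excludes patients with creatinine clearance below 50 mL/min or creatinine above 1.3 mg/dL. Section N expects 10-20% of patients to be women.

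**The concern.** The factor conflicts with the plan's own entry rule. A woman must have a measured clearance of at least 50 to enrol, yet the formula gives her a GFR typical of advanced renal failure. A value below 25 cannot fall by 25, so item 1 has no effect in women. Under item 2, a value that is abnormal at every visit cannot separate a woman with renal injury from one without.

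The plan names renal impairment as a major safety concern with tenofovir, and both arms take the drug for 192 weeks or longer. If the printed equation is applied, the only criterion tied to a numeric GFR decline works in men and not in women.

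**Working it through.** **Inputs from the documents.** The equation as printed; the female factor .0762; the race factor 1.180; the decline of 25; entry limits of creatinine ≤1.3 mg/dL and albumin ≥3 g/dL (Section B); Grade 2 creatinine >1.5 × ULN (Appendix B). The plan states no GFR value for any patient, so there is no figure of its own to reproduce.

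**Assumed inputs.** Typical patient: age 45, SUN 14 mg/dL, albumin 4.0 g/dL, race term off. Grid for ranges of the rise: age 25/45/65, SUN 10/14/20, albumin 3.5/4.0/4.5. Grade 2 is evaluated at an assumed ULN of 0.9 to 1.1 mg/dL. A factor of 0.762, a one-place decimal shift, is used for comparison only; the documents do not give it.

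**Formula.** GFR = 170 × Cr^-0.999 × age^-0.176 × SUN^-0.170 × Alb^0.318 × F.

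At Cr 1.0 the typical inputs give 170 × 0.5117 × 0.6385 × 1.5540 × F = 86.3 × F. The creatinine at which item 1 is met solves GFR(Cr) = GFR(baseline) − 25.

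| F | Baseline Cr | Baseline GFR | Cr at a fall of 25 | Rise needed (grid range) |
|---|---|---|---|---|
| 1 (man) | 0.8 | 107.9 | 1.042 | 0.24 (0.19-0.30) |
| 1 (man) | 0.9 | 95.9 | 1.218 | 0.32 (0.25-0.40) |
| .0762 (woman, as printed) | 0.8 | 8.2 | none | not reachable |
| .0762 (woman, as printed) | 0.9 | 7.3 | none | not reachable |
| 0.762 (woman, assumed) | 0.8 | 82.2 | 1.150 | 0.35 (0.27-0.45) |
| 0.762 (woman, assumed) | 0.9 | 73.1 | 1.369 | 0.47 (0.35-0.61) |
| 0.762 (woman, assumed) | 1.0 | 65.8 | 1.614 | 0.61 |

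**Item 1, printed factor.** Doubling a woman's creatinine from 0.8 to 1.6 lowers her calculated GFR by 4.1 (8.2 to 4.1). The same change in a man lowers it by 53.9 (107.9 to 54.0). Her baseline creatinine would have to be about 0.26 for GFR even to equal 25. Over creatinine 0.5-1.3, age 19-80, SUN 6-25 and albumin 3.0-5.2, with the race term on or off, women's values run from 3.8 to 22.7. Baselines above 25 appear only at creatinine below roughly 0.3 to 0.5, depending on the other inputs.

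**Item 2, printed factor.** All of these values lie below 30, 50, 60 and 90, so the flag is abnormal for every woman at any of those cut-offs.

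**What item 3 covers.** With 0.762, a woman starting at 0.8 would meet item 1 before a 0.5 rise at every grid point. From 0.9 the typical rise is just short of 0.5 (0.47), and 9 of the 27 grid points exceed it. From 1.0 item 3's rise comes first with typical inputs.

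A 0.5 rise alone brings only weekly monitoring. The permanent stop needs creatinine above 1.35, 1.50 or 1.65 for a ULN of 0.9, 1.0 or 1.1. For a woman starting at 0.8, GFR with 0.762 would by then have fallen from 82.2 to 48.7, 43.9 or 39.9.

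**The case against.** The strongest reply is that this is a character slip in a named equation. The intent is clear, and nothing shows that anyone computed GFR with .0762. A baseline GFR of about 8 in a woman with measured clearance of at least 50 would be noticed, not least at the weekly safety review in Section L. That is fair, and it makes the harm conditional. It does not make the written rule usable. The extracted text also cannot show whether the slip is in the protocol itself or arose when the PDF was read.

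A second point is that women remain covered in other ways:

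- item 3;
- urine glucose, phosphate and urinalysis as separate triggers under item 2;
- 24-hour clearance within the item 2 evaluation and at weeks 48 and 192;
- the general stopping statement in Section F;
- the dosing-interval statement for clearance below 50.

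This stands and limits the consequence. Item 2, taken literally, errs towards more checking rather than less. But none of these replaces a numeric criterion for GFR decline.

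Third, item 2 states no cut-off. If abnormal meant change from baseline, the claim that every woman is flagged would fail. It holds for any plausible fixed limit.

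Fourth, item 1 clearly acts before item 3 only when a woman's baseline creatinine is about 0.8 or lower. That is correct, and the documents give no creatinine distribution. The slip does not touch randomisation, the primary endpoint or its analysis.

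**Conclusion.** The concern holds: the factor is wrong as written, and the entry rule shows this without any outside source. With the printed formula, item 1 cannot be met by any woman with a realistic creatinine, and item 2's calculated-GFR flag carries no information for women under any plausible fixed cut-off. About 10 to 20 of 100 patients are affected (10-20% × 100).

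The practical loss is an earlier trigger for women with low baseline creatinine, with partial backup from the other renal rules. The result for item 1 rests on creatinine of 0.5 or more and the stated ranges for age, SUN and albumin. The comparison with a working criterion rests on the assumed 0.762. Whether any patient was affected depends on whether .0762 was actually used, which the documents do not show. This should be corrected, but it does not threaten the trial's main comparison.

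**What to change.** Check the female factor against the source equation and correct it in item 1. A value of 0.762 gives plausible results (about 82 at creatinine 0.8), but it is an assumption to be verified. If the clinical laboratory reports GFR from its own coded equation, cite that equation in item 1 in place of the printed one.

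If the printed factor was used for any enrolled woman, recalculate her baseline and follow-up GFR and reapply items 1 and 2. The inputs are already in the Section E chemistry panel: "BUN, creatinine, albumin, total protein, calcium, and phosphate".

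The cost is one constant in one formula, plus a recalculation only if the printed factor was used. No new visits or samples are needed.
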